### ***5.5 Subject Status and Classification***

#### Enrolled Cohort

A subject will be considered enrolled when the ICF is signed.

#### Intent-to-treat Cohort

The intent-to-treat (ITT) cohort is defined as all subjects who signed the ICF, were evaluated for inclusion/exclusion criteria, and in whom the endoscopic procedure was initiated.

#### Treated Cohort

The treated cohort is defined as all ITT subjects who have an AXIOS™ stent implanted for the purpose of WON drainage. Subjects in the treated cohort will be counted towards the enrollment ceiling and this cohort will be considered the primary analysis cohort.

#### Per Protocol Cohort

The per-protocol cohort is defined as all treated subjects for whom an AXIOS™ stent was implanted for the purpose of WON drainage and met all eligibility criteria.

### ***5.6 End of Study Action Plan***

Subjects will have the study test device, the AXIOS™ Stent, implanted temporarily for up to 60 days. A subject will be considered lost to follow-up if the subject remains unresponsive to communication after three documented attempts by study staff. However, for those subjects who remain unresponsive to communication while the stent remains in place, additional attempts will be made to request the subject's return for study stent removal. These additional attempts may include increased telephone and written communications and contact with the subject's primary care physician (if this communication is consented to in the Informed Consent Form).

## 6 Study Methods

### 6.1 Data Collection

Procedure/ Assessment	Screening/ Pre-Op Visit	Stent Placement Procedure	WON Resolution Assessment Visit (7 (+/- 3 days) /14 (+/- 5 days) for inpatients/outpa tients)	Reintervention / Necrosectomy Visit (when needed)	Stent Removal Visit (14 -60 days from stent placement)	7 Day Post Stent Removal Visit (+/- 3 days)	WON Recurrence Assessment Visit/End of Study (6 months (+/- 14 days) from stent removal)
Informed Consent	X						
Eligibility Criteria	X						
Demographics	X						
Etiology of AP	X						
Onset of AP	X						
Severity of AP	X						
WON related symptoms	X		X				X
Imaging +++	X +		X	X **			X **
Organ Failure	X		X		X		
Quality of Life (SF-12)	X *				X		X
Laboratory Tests	X	X ++	X **	X **			X **
Current Medication	X	X ***	X ***	X ***	X ***	X ***	X ***
Stent Placement		X					
Lavaging of WON and/or placement of Nasocystic Drain		X **					
Stent Lumen Patency		X		X	X		
Necrosectomy				X **			
Percutaneous or Additional Endoscopic Drainage				X **	X **		
Stent Removal					X		
Adverse Event Assessment		X	X	X	X	X	X
Device Event Assessment		X	X	X	X		

X = Required

\* = If the SF-12 is not done due to the condition of the patient, this will not be considered a protocol deviation

\*\* = As needed per standard of care

\*\*\* = Documentation of any changes in medication since previous visit

+ = Imaging should be done within 2 weeks of the initial drainage procedure

++ = Labs need to be repeated at this visit ONLY IF they were collected more than 3 days before the stent placement procedure.

+++ = Imaging may include CT with contrast (unless contraindicated), MRI, EUS

## Study Candidate Screening

No study-specific testing will be conducted until after the subject has signed an ICF. A Screen Failure/Enrolled Log will be maintained in the Electronic Data Capture (EDC) system by the center to document select information about candidates who signed consent.

## 6.2 Informed Consent

Written Informed Consent must be obtained for all subjects who are potential study candidates. Subjects will be asked to sign the ICF before any study-specific tests or procedures are performed. The ICF is study-specific and must be approved by the study IRB/EC and Competent Authority (CA), as applicable. Study personnel should explain that even if a subject agrees to participate in the study and signs the ICF, the EUS procedure may demonstrate that the subject is not a suitable candidate for the study.

## 6.3 Visit Schedule

### Screening / Pre-op Visit – Office/Hospital Visit:

- Informed Consent
- Demographics
- Etiology of AP
- Onset date of AP
- WON related symptoms
- CT Scan or MRI (identification of percentage of necrosis and confirmation of absence of pseudoaneurysms inside WON)
- Organ failure assessment (Marshall scoring system)
- Severity of AP
- Labs
- Quality of Life (SF-12)  
*Note: If the SF-12 is not done due to the condition of the patient, this will not be considered a protocol deviation*
- Current medication

### Stent Placement Procedure – Office/Hospital Visit

- AXIOS™ stent placement  
*Note: Physicians will select the site of the AXIOS™ stent placement under endoscopic guidance and choose an access location that is free from necrotic debris and intervening blood vessels, where the wall between the GI tract and fluid collection is 10mm or less,*

*and where it is possible to place the AXIOS™ stent in a position such that the inner flange (inside WON) has enough space to expand.*

- Lavaging of WON under endoscopic visualization and/or placement of nasocystic drain, or a single, 7fr double pigtail plastic stent (Boston Scientific 7Fr Advanix™ Biliary Stent) through the AXIOS™ stent at the discretion of investigator
- Stent lumen patency assessment
- Adverse event assessment/device event assessment
- Current medication
- Labs (as needed)

*Note: Labs need to be repeated at this visit ONLY IF they were collected more than 3 days before the stent placement procedure.*

**Multiple Interventions During Index Procedure:**

Once stent is placed into the WON, dilation of the AXIOS™ stent is allowed to expand the stent if needed. Dilation can be performed to the maximal diameter of the AXIOS™ stent. A single, 7 fr double pigtail plastic stent (Boston Scientific 7Fr Advanix™ Biliary Stent) may be placed through the AXIOS™ stent at the discretion of the investigator. Access to the WON with a forward viewing diagnostic or therapeutic upper gastroscope is allowed up to 20 minutes (from time of endoscopic access of the WON) to break-up large chunks of necrosis and lavage collection at the discretion of the physician.

WON Resolution Assessment - 7 days (+/- 3 days) for inpatients and 14 (+/- 5 days) days for outpatients (needed until radiographic decrease of WON size to  $\leq$  3cm) – Office/Hospital Visit:

- Cross sectional imaging (CT or MRI) to assess reduction in WON size. If reduction in size is deemed insufficient, necrosectomy will be initiated
- Documentation of clinical improvement defined as improvement of principal WON-related symptoms
- Necrosectomy (as needed)
- Adverse event assessment/device event assessment
- Organ failure assessment (Marshal scoring system)
- Current medication
- Labs (as needed)

Reintervention/Necrosectomy Visits when needed during AXIOS™ stent indwell – Office/Hospital Visit:

- Necrosectomy initiated if WON reduction in size is deemed insufficient during WON Resolution Assessment Visit. Duration of each necrosectomy session is limited to 60 minutes
- Percutaneous drainage or additional endoscopic drainage may be needed if reduction in WON size is insufficient or in cases of continued WON related symptoms such as infection/sepsis despite necrosectomy. Choice of stent (AXIOS™ or plastic double pigtail

stent(s)) for repeat endoscopic drainage procedures will be left to the discretion of the investigator. The double pigtail plastic stent(s) or new AXIOS™ stent may be placed through the tract established by the original AXIOS™ stent or in a separate location.

- Stent lumen patency assessment
- Imaging (as applicable)
- Labs (as needed)
- Adverse event assessment/device event assessment
- Current medication

Stent Removal Visit - between 14 days and 60 days (+/- 7 days) of stent placement – Office/Hospital Visit

- Stent lumen patency assessment
- Stent removal after evidence of clinical and radiographic (via CT or MRI) resolution of WON

*Note: Removal of stent by 60 days is required if WON not resolved. Patients with unsuccessful or incomplete WON resolution by 60 days will proceed to standard of care treatment outside of this protocol after removal of the AXIOS™ stent; however, the patient outcome will continue to be followed. Alternative interventions may include surgery, endoscopic drainage with double pigtail plastic stents, percutaneous catheter drainage and necrosectomy (video-assisted retroperitoneal debridement (VARD), or endoscopic transluminal debridement, or open necrosectomy).*

- Adverse event assessment/device event assessment
- Organ failure assessment (Marshal scoring system)
- Quality of Life (SF-12)
- Current medication

7 Day (+/-3 days) Post Stent Removal Visit – (Office or phone call):

- Adverse Event assessment
- Current medication

WON Recurrence Assessment Visit/End of Study – at 6 Months (+/- 14 days) from stent removal:

- Recurrence assessment (presence of clinical symptoms and further diagnosis per standard of care (e.g. labs and imaging))
- Adverse Events assessment
- Quality of Life (SF-12)
- Current medication

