migration by apposing the WON wall to the stomach or duodenal wall. This could result in faster resolution of the WON using fewer endoscopic procedures. Rinninella et al, performed a retrospective study examining the drainage of PFCs, including WON. They included 93 patients with PFCs (80% with complex collections) who underwent drainage with AXIOS™, 52 of whom had WON. Among those with WON, the solid component was judged to be less than 25% of the collection in 14 patients, between 25% and 50% in 20 patients, and more than 50% in the remaining 18 patients. Clinical success, resolution of PFCs without the need for additional endoscopic or percutaneous drainage procedures or surgery, was achieved in 47 of 52 patients (90.4%) with WON [26]. A separate study performed by Shah et. al. prospectively analyzed patients with chronic pancreatitis who received treatment of pancreatic pseudocysts or WONs using AXIOS™. They concluded that the large lumen size of the metal stent allows for successful necrosectomy through the stent when needed [27].

The current study is proposed to supplement this literature by documenting the safety and effectiveness of the AXIOS™ lumen apposing self-expandable metal stent system for the drainage of WON containing greater than 30% necrotic material.

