### **5.2 Exclusion Criteria**

Subjects who meet any one of the following criteria will be excluded from this clinical study.

1. Pseudocyst
2. Cystic neoplasm
3. Untreated Pseudoaneurysm  $>$  1cm within the WON
4. More than one WON clearly separated and requiring drainage

5. WONs that require dual modality interventions (endoscopic and percutaneous) from the beginning (i.e. deep paracolic space involvement that is inaccessible through the central drainage access)
6. Prior surgical, interventional radiology or endoscopic procedures for the treatment of the WON
7. Abnormal coagulation:
  - INR > 1.5 and not correctable
  - presence of a bleeding disorder
  - platelets < 50,000/mm^3
8. Intervening gastric varices or unavoidable blood vessels within the access tract (visible using endoscopy or endoscopic ultrasound)
9. WON that poorly approximates the GI lumen ( $\geq 1$ cm away)
10. Pericolic gutter necrosis
11. Pelvic necrosis
12. Prior true anaphylactic reaction to contrast agents, nitinol (nickel titanium), silicone or any other materials contacting the patient
13. Female of childbearing potential with a positive pregnancy test prior to the procedure or intends to become pregnant during the study
14. Currently participating in another investigational drug or device study that has not completed the primary endpoint or that clinically interferes with the endpoints of this study

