## **7 Statistical Considerations**

### **7.1 Effectiveness Endpoint**

#### Primary Effectiveness Endpoint:

The primary effectiveness endpoint for this study is the resolution of WON with endoscopic drainage defined as radiographic decrease of WON size to  $\leq 3$ cm evaluated by CT scan or MRI

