#### Primary Effectiveness Endpoint Assessment:

*Note: Success will be based on the number of WONs resolved, not on the number of AXIOS™ Stents required to achieve resolution.*

- If it is determined that the fluid collection is actually two separate collections, and each collection is drained via an AXIOS™ stent, then each collection will be assessed individually via the drainage success criteria of  $\leq 3$ cm.
- If it is determined that the fluid collection is a single collection but the drainage is inadequate via a single AXIOS™ stent, then the success of the AXIOS™ drainage will be assessed as follows:
  - If a second AXIOS™ stent is used at a new drainage site/original drainage site and the entire fluid collection is drained to meet the success criteria of  $\leq 3$ cm then the collection will be considered to be a single collection drainage success.
  - If a second AXIOS™ stent is used at a new drainage site and the entire fluid collection does not drain adequately to meet the drainage success criteria of  $\leq 3$ cm then the fluid drainage of the collection will be considered to be a single drainage failure.
  - If a plastic stent is used at a new drainage site and the entire fluid collection drains to meet the drainage success criteria of  $\leq 3$ cm then the fluid drainage will be considered indeterminate.

- If a single, 7fr plastic stent is used at the same drainage site, through the AXIOS™ stent, and the entire fluid collection drains to meet the drainage success criteria of  $\leq 3$ cm then the fluid drainage will be considered a single collection drainage success.
- If a plastic stent is used at a new drainage site and the entire fluid collection does not drain to meet the drainage success criteria of  $\leq 3$ cm then the fluid drainage will be considered a single drainage failure.

Hypothesis:

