#### Effectiveness Endpoint Success Criteria

An observed rate of 67% or higher for the proportion of AXIOS patients with reduction of WON size to  $\leq 3$ cm within 60 days from AXIOS™ stent placement is required for success.

This rate is the same as the point estimate of the random-effect meta-analysis of WON resolution rates provided in Table 7.1. Note that in the recent systematic review and meta-analysis [28] (Appendix I in Section 21) WON resolution rates were higher and number of procedures required to reach WON resolution were lower when using LAMS compared to plastic stents for WON drainage. Thus the proposed success criteria for effectiveness seems reasonable.

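### Percutaneous drainage is permitted while the AXIOS stent is in place, but no rule scores it for the primary endpoint, and the endpoint wording and the 67% success criterion point in different directions

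*Protocol*

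**What the plan says.** **Permission.** Protocol section 6.3, under "Reintervention/Necrosectomy Visits when needed during AXIOS™ stent indwell", states: "Percutaneous drainage or additional endoscopic drainage may be needed if reduction in WON size is insufficient". Persisting symptoms after necrosectomy are a second stated reason. The synopsis repeats this. The schedule in section 6.1 has a row, "Percutaneous or Additional Endoscopic Drainage", marked as needed at the reintervention and stent removal visits. Exclusion 5 in section 5.2 removes only "WONs that require dual modality interventions (endoscopic and percutaneous) from the beginning", so later percutaneous drainage in an eligible patient remains possible.

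**Scoring rules.** Protocol section 7.1 opens its list for inadequate drainage with "If it is determined that the fluid collection is a single collection but the drainage is inadequate via a single" AXIOS stent. The items that follow deal with a second AXIOS stent and with plastic stents. The synopsis, SAP section 1 and SAP section 3.1 carry similar lists; the SAP lists lack the Protocol's item on a 7 Fr plastic stent through the AXIOS stent. None of the four mentions a percutaneous catheter.

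**Endpoint and numerator.** Protocol section 7.1 defines the endpoint as "resolution of WON with endoscopic drainage defined as radiographic decrease of WON size to" 3 cm or less on CT or MRI. The statistical methods in 7.1 and SAP section 3.1.2 keep the endoscopic qualifier in the numerator. The denominator is every patient with a successfully implanted AXIOS stent.

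**Success criterion.** Protocol section 7.3, the synopsis and SAP section 3.3.1 require an observed rate of at least 67% "for the proportion of AXIOS patients with reduction of WON size to" 3 cm or less within 60 days of placement. No drainage route is named.

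**The concern.** The study objective is to show that lumen-apposing metal stents are effective. Consider a patient whose collection does not shrink enough through the AXIOS stent, who receives a percutaneous catheter while the stent is still in place, and whose scan within 60 days shows 3 cm or less. The care is permitted and the scan is in time, but the primary endpoint has no label for the result.

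The sponsor recognised the same problem for another rescue: a plastic stent at a new site that brings the collection to 3 cm or less is scored as indeterminate, not as a success. A percutaneous catheter is likewise drainage outside the study stent through another route, yet it has no entry. With no rule, someone must choose the scoring after the outcomes are known, in an open-label single-arm study whose verdict rests on a point estimate against a fixed threshold.

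**Working it through.** **1. The plan's own figure.** The 67% threshold is the random-effects pooled rate in Protocol Table 7.1. From the seven x/N pairs (45/61, 31/45, 28/53, 50/81, 85/112, 27/36, 36/60; total N = 448), take y = ln[x/(n−x)] with variance 1/x + 1/(n−x) and pool by DerSimonian-Laird. This gives Q = 13.30, tau² = 0.091 and a back-transformed rate of 67.0% (60.0% to 73.4%), as stated. The threshold reproduces; the issue is what counts towards it.

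**2. The texts side by side, for a catheter-assisted resolution within 60 days.**

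| Text | What it asks for | Direction |
|---|---|---|
| Endpoint and numerator (Protocol 4.1, 7.1; SAP 3.1, 3.1.2) | Resolution with endoscopic drainage | Against counting it |
| Words after the definition in the same sentence | Size of 3 cm or less on CT or MRI | Silent on route |
| Success criterion (synopsis, Protocol 7.3, SAP 3.3.1) | Size of 3 cm or less within 60 days | For counting it, if read literally |
| Nearest scoring rule (plastic stent, new site, drained) | Indeterminate | Against counting it |

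**3. Pass mark.** 0.67 × 40 = 26.8, so 27 successes are needed. 27/40 = 67.5% passes; 26/40 = 65.0% fails.

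**4. Effect of the scoring choice.** Let R patients reach 3 cm or less by any route within 60 days, of whom k did so only with percutaneous help. The rate is R/40 if they count as successes, (R−k)/40 if they do not count but stay in the denominator, and (R−k)/(40−k) if they are dropped.

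| R | k | Counted | Not counted, kept | Dropped |
|---|---|---|---|---|
| 27 | 1 | 67.5% pass | 26/40 = 65.0% fail | 26/39 = 66.7% fail |
| 28 | 1 | 70.0% pass | 27/40 = 67.5% pass | 27/39 = 69.2% pass |
| 28 | 2 | 70.0% pass | 26/40 = 65.0% fail | 26/38 = 68.4% pass |
| 30 | 4 | 75.0% pass | 26/40 = 65.0% fail | 26/36 = 72.2% pass |

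Counting and not counting (with the patient kept) give different verdicts whenever R ≥ 27 and k ≥ R − 26. One patient suffices at R = 27 and two at R = 28, which is the plan's expected 70%. The R = 28, k = 2 and R = 30, k = 4 rows show that denominator handling matters too.

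**5. Chance of passing, as an illustration.** P(pass) = P(X ≥ 27), X ~ Binomial(40, p). Two assumptions are not in the documents: that the expected 70% is the rate by any route, and the share f of all patients who reach 3 cm or less only with percutaneous help. If those patients count, P(pass) = 0.703 throughout. If they do not, p = 0.70 − f:

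| f | p | P(pass) |
|---|---|---|
| 0 | 0.700 | 0.703 |
| 2.5% | 0.675 | 0.574 |
| 5% | 0.650 | 0.441 |
| 10% | 0.600 | 0.211 |
| 15% | 0.550 | 0.075 |

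**The case against.** The strongest reply is that the plan already excludes these cases. The endpoint says with endoscopic drainage, the numerator repeats it, and the criterion can be read as a threshold on that endpoint and not as a new definition. This stands in part. A reader might infer that the plan scores a catheter-assisted resolution as an AXIOS success; the documents do not support that as a settled reading. It follows only if the criterion is taken literally and alone. But the reply does not close the gap: what follows the definition is purely a size measurement, the pass/fail rule omits the route, and no listed rule decides the case.

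Four further points stand.

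- The documents give no frequency for percutaneous drainage, and the exclusions for inaccessible paracolic extension, gutter necrosis and pelvic necrosis may make it uncommon. Nothing in them shows that it is commoner in collections with more solid content.
- A reader might infer a bias in favour of the device against the benchmark. Counting these cases can only raise the raw rate, but the documents do not say whether the seven plastic-stent series counted percutaneous-assisted resolution, so the net effect on the comparison is unknown.
- The AXIOS series cited in Protocol section 1 defined success as "resolution of PFCs without the need for additional endoscopic or percutaneous drainage procedures or surgery". That also bars repeat endoscopic drainage, whereas this plan can score a second AXIOS stent as a success. The series shows that percutaneous rescue is a recognised scoring question; it is not a standard that this plan adopts.
- Treating the case as not a success is a choice, and percutaneous drainage may be done for persisting symptoms as well as for size. The choice does, however, follow the endpoint's own words. Among all implanted patients, an indeterminate patient kept in the denominator gives the same figure, 26/40 in the first row of the table.

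**Conclusion.** The concern holds as a conflict and a gap. A permitted, foreseeable intervention has no primary-endpoint score, and the endpoint definition and the success criterion give different answers for it. That one patient can reverse the verdict is arithmetic, but only when exactly 27 of 40 reach the size limit by any route; at 28 it takes two. The probabilities in step 5 are illustrations that depend on assumed shares, not forecasts. A reader might take the fall from 0.703 to 0.211 as the size of the problem; that figure requires 10% of patients to resolve only with percutaneous help, which no document states. This goes beyond missing detail, because two stated rules disagree on the quantity that decides the study, and they should be reconciled before the data are analysed.

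**What to change.** Change the scoring text only; permitted care stays as written.

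1. In the success criterion (synopsis, Protocol 7.3, SAP 3.3.1), restore the words with endoscopic drainage, so that it matches the endpoint.
2. Add one item to the assessment rules in the synopsis, Protocol 7.1, SAP section 1 and SAP 3.1: a collection that reaches 3 cm or less only after percutaneous or surgical drainage or debridement is not a success for the primary endpoint or the 67% criterion, and the patient stays in the denominator of all implanted patients.
3. State in the same item that endoscopic necrosectomy does not affect the score.
4. Report the rate that counts these patients as resolved as a supportive figure, with the number affected.

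The cost is a few sentences in each document. The schedule already lists percutaneous drainage by visit, so no new procedure or visit is needed. The downside is that the observed primary rate may be slightly lower.
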